### **3 STUDY OBJECTIVE(S) AND DESIGN**

#### **3.1 Study Objective(s)**

The primary objective is to compare the time to prostate cancer progression (pathological or therapeutic progression) between subjects treated with enzalutamide versus subjects undergoing active surveillance.

The secondary objectives are to evaluate:

- Safety
- Proportion of subjects with negative biopsy for cancer at 1 year and 2 years
- Percent of cancer positive cores at 1 year and 2 years
- Time to PSA progression (secondary rise in serum PSA $\geq$ 25% above baseline or  $\geq$ 25% above nadir or absolute increase  $\geq$  2 ng/mL)
- Proportion of subjects with secondary rise in serum PSA $\geq$ 25% above baseline or  $\geq$ 25% above nadir or absolute increase  $\geq$  2 ng/mL at 1 year and 2 years
- Brief fatigue index (BFI)
- Medical outcomes study 12-item short form survey (SF-12)
- Expanded Prostate Cancer Index Composite (EPIC) questionnaire- urinary, sexual and hormonal domains
- Memorial Anxiety Scale for Prostate Cancer (MAX-PC) questionnaire

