**CCI**

#### **3.2 Study Design**

This is a multicenter, randomized, open label exploratory study, conducted in the US and Canada, evaluating the efficacy and safety of enzalutamide for extension of time to prostate cancer progression (pathological or therapeutic) in subjects with clinically localized, histologically proven prostate cancer that is categorized as low risk or intermediate risk and who are under AS. A total of 222 subjects from approximately 50 centers will be enrolled. Subjects are eligible if they were diagnosed within 6 months of screening and have been on AS. A minimum of ten cores from transrectal ultrasound-guided prostate biopsy (mpMRI targeted versus non-mpMRI targeted) are required; confirmatory biopsy before entering the study is not required and is done at the discretion of the investigator.

Low risk is defined as T1c-T2a, PSA $<$ 10, N0, M0 (or presumed N0, M0 if computerized tomography [CT]/bone scan not done due to low risk of metastases), GS  $\leq$  6, ECOG status  $\leq$  2 and estimated life expectancy  $>$  5 years. Intermediate risk is defined as T2b-T2c, PSA $<$ 20, N0, M0 (or presumed N0, M0 if CT/bone scan not done), GS  $\leq$  7 (3+4 pattern only), ECOG status  $\leq$  2 and estimated life expectancy  $>$  5 years.

Prostate cancer progression is defined as either therapeutic progression or pathological progression. Therapeutic progression is defined as the earliest occurrence of primary therapy for prostate cancer (prostatectomy / radiation / focal therapy / systemic therapy). Pathological progression is defined as increase in primary or secondary Gleason pattern by  $>$  1 or higher

proportion of cancer positive cores (>15% increase). Subjects will be stratified by low versus intermediate risk and type of biopsy performed (mpMRI targeted versus non-mpMRI targeted).

Subjects will be randomized (1:1) either to receive treatment with enzalutamide (160 mg), administered as four 40 mg capsules, by mouth, once daily or to AS during the one year study treatment period. Following the one year treatment period, all subjects will be followed for one additional year. Subjects will be followed up every 3 months for these 2 years, after which follow-up will either be every 6 months or unscheduled until the last subject finished their 2 year follow-up. Serum PSA will be measured at baseline and every 3 months during subsequent follow-up visits.

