#### **6.1.2 Secondary Efficacy Endpoints**

The secondary endpoints are:

- Safety
  - Adverse events / treatment-emergent adverse events
  - Clinical laboratory variables (hematology, biochemistry including liver enzymes and total bilirubin)
  - Vital signs (systolic and diastolic blood pressure and pulse rate)
  - 12-lead electrocardiogram (ECG)
  - Physical examination assessments
- Incidence of negative biopsies for cancer at 1 year and 2 years
- Percent of cancer positive cores at 1 year and 2 years
- Time to PSA progression (secondary rise in serum PSA $\geq$ 25% of baseline or  $\geq$ 25% above nadir or absolute increase  $\geq$ 2ng/mL)
- Incidence of secondary rise in serum PSA $\geq$ 25% baseline or  $\geq$ 25% above nadir or absolute increase  $\geq$ 2ng/mL at 1 year and 2 years
- BFI
- SF-12 assessments
- EPIC questionnaire (urinary, sexual and hormonal domains)
- MAX-PC questionnaire

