## 6.4 Other Variables

To clearly state, the following variables are defined:

- Month = 30.4375 days. Year = 365.25 days.
- $BMI(kg/m^2) = Weight(kg) / Height(m^2)$
- Age at randomization=  $\text{floor}((\text{intck}(\text{'month'}, \text{birth date}, \text{randomization date}) - (\text{day}(\text{randomization date}) < \text{day}(\text{birth date}))) / 12)$
- Time since initial/histological diagnosis (years) =  $[(\text{date informed consent signed} - \text{date of initial/histological diagnosis}) + 1] / 365.25$ .
- Time since initial diagnosis to Randomization (years) =  $[(\text{date of Randomization} - \text{date of initial diagnosis}) + 1] / 365.25$ .
- The duration of treatment was calculated as the (last dose date – first dose date) + 1.
- Number of pills taken from one visit to the next = number of pills dispensed – number of pills returned.
- Study drug compliance at each visit is calculated as =  $[(\text{number of pills dispensed} - \text{number of pills returned}) / (4 * \text{number of days in the visit period})] * 100$ .
- Baseline results are defined as the last assessment prior to first dose of study drug, for subjects randomized to once daily enzalutamide. For subjects randomized to active surveillance, baseline is defined as the last assessment prior to or on the date of randomization.
- Treatment Emergent Adverse Events (TEAEs) are any AEs occurring on or after date of first study drug dose date (or randomization for AS) until 30 days post-treatment end date (or 1-year plus 30 days for AS).
- Treatment Phase is defined as date of first study drug dose (or randomization for AS) until either 30 days post treatment end date or (if earlier) study discontinuation date.
- 1-Year Follow-Up Phase is defined as 31 days post treatment end date until either completing 1-Year Follow-Up or (if earlier) study discontinuation date.
- Continued Follow-Up Phase is defined as the day after completing 1-Year Follow-Up phase until study discontinuation date.

Study Day is defined using the following step-wise function:

- If date of interest is on or following randomization, Study Day = Date of Interest – Randomization Date + 1;
- Else, Study Day = Date of Interest – Randomization Date.

Change from baseline is the difference between the result on a post baseline visit and baseline assessment.

Rise in serum PSA is defined as  $PSA \geq 25\% \text{ of baseline or } \geq 25\% \text{ above nadir or } \text{absolute increase} > 2\text{ng/mL}$ .

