### **7.4.2 Analysis of Secondary Endpoints**

#### **7.4.2.1 Cancer Biopsy Incidence and Secondary Rise in PSA**

The incidence of negative biopsy for cancer and secondary rise in serum PSA will be summarized with frequencies and percentages at one and two years by treatment group, subgroups and overall.

Treatment comparisons will be performed using the exact binomial distribution as well as the normal approximation to the binomial distribution. Inferences will include 95% confidence intervals of the odds ratio for each endpoint between treatment groups at both Year 1 and Year 2 for biopsies and for each of Years 1 and 2 and end of study for PSA. Comparison between enzalutamide and AS will be evaluated by logistic regression using the treatment groups, randomization stratification factors [prostate cancer risk (low/intermediate), type of biopsy performed (mpMRI targeted/non mpMRI targeted)], age, race, and time since prostate cancer diagnosis as fixed effects and site and subject as random effects.

Time to PSA progression will be analyzed with the same methods as detailed for the primary endpoint analysis in Section 7.4.1.

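### SAP section 6.4 sets the PSA-rise threshold at 25% of baseline where section 3.1 sets it at 25% above baseline; coded as written, a stable or halved PSA counts as a rise

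*SAP*

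**What the plan says.** The baseline part of the PSA criterion is worded in three ways, over three sections of the SAP.

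- Section 3.1 (objectives), for both time to PSA progression and the proportion with a rise: "secondary rise in serum PSA $\geq$ 25% above baseline or".
- Section 6.1.2 (secondary endpoints), for time to PSA progression: "secondary rise in serum PSA $\geq$ 25% of baseline or".
- Section 6.1.2, for incidence: "Incidence of secondary rise in serum PSA $\geq$ 25% baseline or".
- Section 6.4 (variable definitions): "Rise in serum PSA is defined as $PSA \geq 25\% \text{ of baseline or". The same sentence goes on to a nadir criterion, which does use the word above, and to an absolute increase in ng/mL.

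The absolute criterion also differs: at least 2 ng/mL in 3.1 and 6.1.2, but strictly more than 2 ng/mL in 6.4.

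Section 7.4.2.1 gives no definition of its own. It compares the incidence of a PSA rise between arms by exact and normal-approximation binomial methods and by logistic regression. For the time-to-event version it says: "Time to PSA progression will be analyzed with the same methods as detailed for the primary endpoint analysis in Section 7.4.1". The legible part of section 8, on departures from the protocol, lists no change to the PSA definition.

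**The concern.** Section 6.4 is where a programmer looks for the derivation. In 6.1.2 the thing being measured is a rise, so a rise of 25% of baseline can be read as an increment and then agrees with 3.1. Section 6.4 does not read that way easily, because it sets the PSA value, not its change, against 25% of baseline. It also uses a different preposition for nadir in the same sentence.

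At stake are two secondary efficacy endpoints: time to PSA progression (Kaplan-Meier and Cox, as for the primary endpoint) and PSA-rise incidence. Under the literal rule, the subjects who escape an early event are those with a deep PSA fall. If such falls are more frequent on enzalutamide, the error is not shared equally between the arms and would look like a treatment effect on PSA progression when no PSA had risen.

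**Working it through.** The SAP gives no figure that depends on this definition, so there is none to reproduce. The check compares the two rules directly.

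**Inputs.** Rule A, 6.4 as written: event if PSA / baseline ≥ 0.25. Rule B, 3.1: event if PSA / baseline ≥ 1.25. Eligibility limits in section 3.2: PSA below 10 (low risk) and below 20 (intermediate risk). PSA schedule in section 3.2: "Serum PSA will be measured at baseline and every 3 months during subsequent follow-up visits". Month 3 target in the schedule of assessments: Study Day 85. Section 6.4: one month = 30.4375 days, and the day of randomization is Study Day 1. Section 4: 222 subjects randomized 1:1, so 222 / 2 = 111 per arm.

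**Step 1: thresholds.** The ratio is 1.25 / 0.25 = 5 at any baseline. The baselines of 4 and 6 are illustrative; 9.9 and 19.9 lie just under the two eligibility limits.

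| Baseline (ng/mL) | Rule A: 0.25 × baseline | Rule B: 1.25 × baseline |
|---|---|---|
| 4 | 1.0 | 5.0 |
| 6 | 1.5 | 7.5 |
| 9.9 | 2.5 | 12.4 |
| 19.9 | 5.0 | 24.9 |

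**Step 2: who is an event at the first post-baseline visit (baseline 6 ng/mL).**

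| PSA (ng/mL) | Change | Rule A | Rule B |
|---|---|---|---|
| 6.0 | none | rise | no rise |
| 3.0 | −50% | rise | no rise |
| 1.5 | −75% | rise | no rise |
| 1.2 | −80% | no rise | no rise |
| 7.5 | +25% | rise | rise |

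In the first three rows neither the nadir criterion nor the absolute criterion is met, so the baseline criterion alone creates the event.

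**Step 3: timing.** (85 − 1) / 30.4375 = 2.76 months. In an arm with stable PSA, every subject would be an event at that visit and the median would be about 2.8 months.

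**Step 4: effect on the nadir criterion.** Under Rule A, the nadir criterion can add an event only if 1.25 × nadir < 0.25 × baseline, that is, nadir < 0.20 × baseline. A check on 2,000,000 random baseline, nadir and PSA triples agreed: the largest nadir/baseline ratio at which it added an event was 0.199.

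**Step 5: possible difference between arms.** The SAP gives no expected PSA response. Let q be the share of the enzalutamide arm with a fall of more than 75% at month 3 (assumed, shown as a range), and take PSA as stable on active surveillance (AS). Rule A events from the baseline criterion are then 111 on AS and 111 × (1 − q) on enzalutamide.

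| Assumed q | AS | Enzalutamide | Difference (percentage points) | Rule B, both arms |
|---|---|---|---|---|
| 20% | 111 | 88.8 | 20 | 0 |
| 50% | 111 | 55.5 | 50 | 0 |
| 80% | 111 | 22.2 | 80 | 0 |
| 95% | 111 | 5.6 | 95 | 0 |

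**Step 6: the 2 ng/mL mismatch.** With the relative criteria as in 3.1, an increase of 2 ng/mL over a reference value r can matter only if r + 2 < 1.25 × r, that is, r > 8 ng/mL. The choice between ≥ 2 and > 2 then changes only a subject whose sole qualifying increase is exactly 2 ng/mL (for example 10 to 12). This is a minor point.

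**The case against.** The strongest reply is that nobody would code the harmful reading. The sentence defines a rise, and under the literal rule the baseline value itself would be a rise, as would a 75% fall. Section 3.1 states the intended threshold twice, the nadir criterion beside it uses the right preposition, and 6.1.2 can be read as an increment. On that reading all the statements agree and no event changes. This is fair as an account of intent, and it is why the point is not graded higher. It does not make the 6.4 sentence correct: a definitions section should not need repair from the objectives before it can be programmed.

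A second reply is that the endpoints concern a secondary rise. If that means a rise after an earlier fall, a subject with stable PSA would not be an event at month 3. The SAP never defines the word, and 6.4 omits it. The month 3 result therefore holds for 6.4 as written, and could be softer if a meaning of secondary were applied from elsewhere.

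Third, the arm differences in step 5 depend on literal coding, uniformly stable PSA on active surveillance, and an assumed response share. That is true. They show what the rule would do and say nothing about how likely it is to be coded that way. Likewise, the nadir criterion is restricted to nadirs below 20% of baseline and is not switched off; some subjects with deep falls would still be caught by it.

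Finally, the study is described as exploratory and only secondary endpoints are involved. That limits the consequence but does not remove the contradiction.

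**Conclusion.** The concern holds. Section 6.4 is wrong as written: its baseline threshold is 0.25 times baseline where the SAP's own objective requires 1.25 times, and nothing elsewhere in the legible text corrects it. Followed exactly, it would count as an event any PSA that has not fallen by more than 75%, from the first post-baseline visit, for two secondary efficacy endpoints that are compared between arms. The fivefold threshold error and the classification of stable or halved PSA values are exact and need no assumption. The size of any spurious treatment difference depends on the PSA response in each arm, which the SAP does not give. If 6.4 is coded as an increment, there is no numerical effect. The primary endpoint and the sample size do not use PSA and are unaffected. The correction should be made, but it does not threaten the main result.

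**What to change.** Restate the definition in section 6.4 with explicit multipliers taken from 3.1: PSA at least 1.25 × baseline, or at least 1.25 × nadir, or an absolute increase of at least 2 ng/mL. Use identical wording in 3.1, both bullets of 6.1.2, and 6.4, which also removes the mismatch between ≥ 2 and > 2. Then confirm that the derivation code for both PSA endpoints uses 1.25 × baseline.

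The cost is one line in 6.4, aligned wording in 6.1.2 and a code check. No new data are needed and the primary analysis does not change. Section 1 of the SAP allows version-controlled revisions before database hard lock. If lock has passed, the code check still applies, and the rule actually used should be stated and justified in the clinical study report.

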Digital rectal examination will be done at baseline and every 6 months during subsequent follow-up visits. All subjects will have transrectal ultrasound-guided prostate biopsy (with or without mpMRI targeting) at 12 months and 24 months with a standard of 12 cores required; two biopsies are required from each target site (if mpMRI is used) as well as 12 systematic biopsies (12 core transrectal ultrasonography [TRUS] guided systematic biopsies including six lateral and six mid lobar cores from the base, middle and apex of the gland) at the same time. All sites will be consistent with their method of biopsy (with regards to the use of mpMRI targeting) throughout the study for all subjects enrolled at that site. If there is a significant clinical reason such as adverse changes on digital rectal examination or increase in PSA, biopsy is allowed based on investigator's decision. If at any time during the study the subject considers intervention for prostate cancer, biopsy is allowed and recommended.

Treatment decisions based on pathological progression are at the discretion of the individual investigator. Hormonal levels (testosterone, DHT, dihydroepiandrosterone, androstenedione and estradiol) will be collected at baseline, 12 months and 24 months. Quality of life/sexual function questionnaires (EPIC), anxiety measures (MAX-PC), BFI, SF-12 assessments will also be done at baseline, 6 months, 12 months, 18 months and 24 months. An additional BFI assessment will be done at 3 months. Subjects who withdraw from the study before the 24 Month visit will be asked to complete the EPIC, MAX-PC, BFI and SF-12 assessments at their final study visit.

Subjects will be followed beyond the two year study period until the last subject has completed the 24 month visit. This additional follow up will entail biannual visits (every 6 months and/or unscheduled visits) that include measurement of serum PSA and digital rectal exam.

All biopsy samples, including those collected for-cause or per standard of care, will be centrally read by a designated pathologist blinded to treatment allocation. CT, magnetic resonance imaging (MRI) and bone scan will be performed at the discretion of the investigator based on clinical need; when performed, these assessments will be read locally and recorded in the electronic case report form (eCRF).

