## 4 SAMPLE SIZE

This study is designed to evaluate time to prostate cancer progression (pathological or therapeutic progression) as the primary endpoint. The overall two-sided type I error for this study is set at 0.05 level. The characteristics of time to prostate cancer progression (pathological or therapeutic progression) are used to determine the total sample size and overall duration.

A sample size of 222 subjects randomized in a 1 to 1 manner accrued over one year, a study duration of 3 years, loss-to follow-up of 16%, an assumed underlying hazard ratio of 0.52 and a three year median time-to-progression for the Control group (0.2310 rate) will result in 72 events (Fleshner et al., 2012). This sample size is sufficient to power this study at 80% with a two-sided type I error rate of 5%.

The assumed hazard ratio of 0.52 is consistent with Fleshner et al. (2012). Specifically, the Fleshner study is powered to detect a 39% failure rate reduction in the treated group with respect to a three year 45% failure rate in the control group. We used a more conservative 30% failure rate reduction for the treated group and a 50% three year failure rate for the control group. This resulted in parameter estimates of 0.2310 for the Control group and 0.1189 for the Treatment group, and thus, resulted in the hazard rate of 0.52.

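### The PSA-rise rule lets one unconfirmed reading above an undefined nadir count as progression, so men with constant PSA can be counted, at a rate that depends on a within-man variability the SAP does not give

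*SAP*

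**What the plan says.** The rule appears three times in the SAP, and none of the three asks for a second reading, a minimum interval, or a minimum absolute rise to accompany the percentage triggers.

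- Section 3.1 (objectives) joins the triggers with *or*: 25% above baseline, then "25% above nadir or absolute increase" of at least 2 ng/mL.
- Section 6.1.2 names the endpoint "Time to PSA progression (secondary rise in serum PSA" and words the baseline trigger as 25% *of* baseline. It also lists the incidence of such a rise at 1 and 2 years.
- Section 6.4 gives the working definition, "Rise in serum PSA is defined as", again with 25% *of* baseline, and with strictly more than 2 ng/mL where 3.1 and 6.1.2 have at least 2 ng/mL.

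On timing, section 3.2 says "Serum PSA will be measured at baseline and every 3 months during subsequent follow-up visits". The schedule of assessments shows PSA at 3, 6, 9, 12, 15, 18, 21 and 24 months. After that, "This additional follow up will entail biannual visits (every 6 months and/or unscheduled visits) that include measurement of serum PSA and digital rectal exam".

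On analysis, section 7.4.2.1 says "Time to PSA progression will be analyzed with the same methods as detailed for the primary endpoint analysis in Section 7.4.1". Section 7.4.1 describes Kaplan-Meier and Cox methods and censoring, and has no confirmation rule. Neither nadir nor secondary rise is defined anywhere.

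**The concern.** The lowest of several noisy readings drifts downwards by chance as readings accumulate. A later reading at the man's true level can then stand 25% above it. When one such reading is enough and there are eight opportunities, a man whose PSA has not changed can be recorded as having PSA progression.

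Two secondary results depend on this definition: time to PSA progression, and the proportions with a rise at 1 and 2 years. If a material share of events is measurement variation, both describe PSA behaviour less well than their names suggest, and the treatment contrast is blurred.

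**Working it through.** **The plan's own figure.** The SAP gives no event count or rate for the PSA endpoint. Its sample-size figure concerns the primary endpoint: with rates 0.2310 and 0.1189 the hazard ratio is 0.5147, and 4 × (1.960 + 0.842)² / (ln 0.5147)² = 31.4 / 0.441 = 71.2, so 72 events, as stated. It reproduces and does not bear on this point.

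**Inputs from the SAP.** Three triggers joined by *or* (3.1, 6.1.2, 6.4); baseline plus eight readings to 24 months (schedule of assessments); no confirmation (6.4, 7.4.1, 7.4.2.1).

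**Assumptions not in the SAP.** Within-man CV of 5% to 15%; log-normal, independent readings; constant true PSA of 6 ng/mL; nadir taken as the lowest value so far, baseline included; the baseline trigger read as 25% *above* baseline; the absolute trigger read as at least 2 ng/mL above baseline.

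**Step 1: one look against baseline.** With σ = √ln(1 + CV²), the chance that one reading is at least 1.25 times baseline is 1 − Φ(ln 1.25 / (σ√2)). At CV 10%, σ = 0.0998, so 0.2231 / 0.1411 = 1.58 and the chance is 5.7%. At CV 5%, 7.5% and 15% it is 0.1%, 2% and about 14%.

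**Step 2: the rule as written, by simulation.** Share of men with constant PSA who meet it at least once:

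| Assumed CV | By 12 months (4 readings) | By 24 months (8 readings) | By 24 months, confirmed at next reading |
|---|---|---|---|
| 5% | 1% | 2% | 0.1% |
| 7.5% | 13% | 32% | 5% |
| 10% | 33% | 66% | 21% |
| 15% | 63% | 92% | 53% |

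Steps 1 and 2 together show that repeated looks against a falling reference, rather than one noisy comparison, produce most of the false events. In the last column, confirmed means the next reading is also at least 25% above the same nadir.

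**Step 3: sensitivity to the assumptions.**

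- True PSA of 4, 8 or 12 ng/mL gives 92% to 94% at CV 15%.
- With nadir taken from post-baseline values only, the nadir trigger alone gives 2%, 27%, 59% and 88% at CV 5%, 7.5%, 10% and 15%.
- With a serial correlation of 0.5 between successive readings, the 66% at CV 10% falls to about 43%.
- If the 1- and 2-year proportions mean status at that visit rather than ever by that visit, the CV 10% figures are 16% at 12 months and 24% at 24 months.

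**Step 4: what confirmation costs.** With an assumed true rise of 15% a year and CV 10%, the share of men with an event by 24 months falls from 98% to about 79% when confirmation is required.

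**The case against.** Several objections have force.

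- *The size rests on an assumed CV.* This stands. The range from 2% to 92% is driven by a quantity the SAP does not give. PSA is read by one central laboratory (schedule of assessments, note 9), which limits assay variation. At CV 5% the problem is negligible.
- *A running nadir is an inference.* This stands as a caveat. An event time has to be fixed from values seen up to that time, so the lowest value so far is the workable reading. If secondary rise was meant to require a real prior decline, fewer stable men on surveillance would qualify. That the text cannot settle this is itself part of the defect.
- *The rule is the same in both arms.* This stands, and it limits the conclusion. A reader might infer that the surveillance curve alone is inflated, that the endpoint there records noise more than rising PSA, or that the hazard ratio cannot be interpreted. The SAP does not support any of these. Visits and triggers are identical in both arms, and proportional variation around a suppressed PSA also crosses 25% above nadir. In an illustration with PSA assumed to fall from 6 to 0.3 ng/mL through month 12 and CV 10%, 24% of treated men have a false event by month 12, against 33% on surveillance. The share of men with truly rising PSA is not given, so noise cannot be ranked against signal.
- *The endpoint is secondary, in a study the SAP calls exploratory.* True. That lowers the priority but does not remove a fault that costs little to mend.

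**Conclusion.** The concern holds in a limited form. The SAP allows one unconfirmed PSA, judged against an undefined nadir and with eight scheduled chances in 24 months, to count as PSA progression. Under a lowest-so-far nadir and independent readings, the false-event share among men with constant PSA is small at CV 5% and about a third or more from CV 7.5% upwards. Positive serial correlation lowers it.

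The supported consequence is a blurred secondary PSA comparison. The size and direction of any hazard-ratio bias were not computed. The primary endpoint and its 72 events are untouched.

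The wording conflict inside the same definition needs no assumption at all. Read literally, 25% *of* baseline is met by almost any stable PSA.

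**What to change.** In section 6.4, carried through to 3.1, 6.1.2 and 7.4.2.1:

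1. Define nadir (for example, the lowest value up to that visit, stating whether baseline counts) and define secondary rise.
2. Use one wording for the baseline trigger, reconciling 25% *of* baseline with 25% *above* baseline, and one inequality for the 2 ng/mL trigger.
3. Require the rise to be met again at the next scheduled PSA, date the event at the first of the two readings, and treat an unconfirmed last value as no event. Apply this to time to PSA progression and to the 1- and 2-year proportions.
4. Report the single-reading version alongside as a sensitivity analysis.

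The cost is SAP wording and programming before database hard lock. Quarterly PSA is already scheduled, so no new sample is needed. The drawbacks should be stated: about 21% false events remain at CV 10% and 53% at CV 15%, and some true rises are delayed or not counted by 24 months, not only those first seen at the last PSA. After 24 months, the next scheduled reading may be six months away.

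### The SAP gives inconsistent event rules for the PSA endpoints: *secondary* rise or plain rise, 25% above or 25% of baseline, and at least 2 or more than 2 ng/mL

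*SAP*

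**What the plan says.** Two secondary efficacy endpoints use the PSA event: time to PSA progression, and the proportion with the event at 1 and 2 years.

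- Section 3.1 lists both, as "Time to PSA progression (secondary rise in serum PSA" and "Proportion of subjects with secondary rise in serum PSA". The limbs are at least 25% above baseline, at least 25% above nadir, or an absolute increase of at least 2 ng/mL.
- Section 6.1.2 repeats both, the second as "Incidence of secondary rise in serum PSA". In the time-to-event item the baseline limb becomes 25% *of* baseline; in the incidence item the preposition is missing. The absolute limb stays at 2 ng/mL or more.
- Section 7.4.2.1 states: "The incidence of negative biopsy for cancer and secondary rise in serum PSA will be summarized with frequencies and percentages". It gives no thresholds. It adds: "Time to PSA progression will be analyzed with the same methods as detailed for the primary endpoint analysis in Section 7.4.1".
- Section 6.4 begins "Rise in serum PSA is defined as" and continues with PSA at least 25% *of* baseline, at least 25% above nadir, or an absolute increase of *more than* 2 ng/mL. The word *secondary* does not appear.

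The SAP does not define *secondary*. It does not say whether the nadir may be the baseline value, or which value the absolute increase is measured from.

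**The concern.** A secondary rise ordinarily means a rise that follows an earlier fall. On that meaning, a man whose PSA goes up from entry and never dips is not an event under three sections, but is one under 6.4. Surveillance subjects receive no study drug, so nothing in the design makes their PSA fall first. An androgen-receptor inhibitor would be expected to lower PSA, so the two readings would be expected to part mainly in the surveillance arm.

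These endpoints are tested, not only described. Time to PSA progression gets Kaplan-Meier and Cox analyses, and the proportions get odds ratios and logistic regression. The Section 8 restriction to descriptive statistics covers the patient-reported outcomes only. The trial is open label, so choosing the event rule once data by arm can be seen would be open to criticism.

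**Working it through.** The SAP states no event rate for PSA, so there is no planned figure to reproduce. The check compares the texts, then applies the competing rules.

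**1. Texts side by side**

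| Section | Name of event | Baseline limb | Absolute limb |
|---|---|---|---|
| 3.1 | secondary rise | ≥25% above | ≥2 ng/mL |
| 6.1.2, time to event | secondary rise | ≥25% of | ≥2 ng/mL |
| 6.1.2, incidence | secondary rise | ≥25% (no preposition) | ≥2 ng/mL |
| 7.4.2.1 | secondary rise | not given | not given |
| 6.4 | rise | ≥25% of | >2 ng/mL |

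The nadir limb is the same wherever it appears.

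**2. One steadily rising series.** Assumed values: baseline 5.0 ng/mL, then 3-monthly readings (the SAP's schedule: "Serum PSA will be measured at baseline and every 3 months during subsequent follow-up visits") of 5.3, 5.7, 6.1, 6.4, 6.7, 7.0, 7.2, 7.4.

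- 25% above baseline, no fall needed: threshold 1.25 × 5.0 = 6.25; first reached by 6.4, so the event is at month 12.
- Earlier reading below 5.0 required: there is none, so he is never an event.
- 25% of baseline, literally: threshold 0.25 × 5.0 = 1.25; the first reading, 5.3, exceeds it, so the event is at month 3.

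**3. The absolute limb.** An increase of 2 ng/mL equals 25% of the reference value when that value is 2 / 0.25 = 8 ng/mL. Below 8 the 25% limb is reached first. The difference between ≥2 and >2 therefore matters only for reference values of 8 or more and a rise of exactly 2, and has little effect.

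**4. Surveillance-arm incidence.** All inputs are assumptions: log-normal reading error with the stated CV, eight 3-monthly readings, limbs of 25% above baseline, 25% above running nadir (baseline included) or +2 ng/mL from baseline. *Fall required* means an earlier reading below baseline.

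| Assumed course | CV | Any rise, 2 years | Fall required, 2 years | Gap (points) |
|---|---|---|---|---|
| Doubling time 3 years, baseline 5 | 5% | 100% | 23% | 77 |
| Doubling time 5 years, baseline 5 | 10% | 98% | 57% | 41 |
| Doubling time 10 years, baseline 5 | 10% | 87% | 62% | 25 |
| Doubling time 10 years, baseline 5 | 5% | 34% | 18% | 16 |
| No growth, baseline 6 | 5% | 2.3% | 1.8% | 0.5 |

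At a doubling time of 10 years and CV 10%, the 1-year figures are 46% and 26%. With 222 / 2 = 111 surveillance subjects, the 25-point gap at 2 years is about 0.25 × 111 ≈ 28 men.

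**5. Does the baseline limb say anything about intent?** Let B be baseline and N the nadir. If a fall below baseline is required, N < B, so any value ≥1.25B is also ≥1.25N and the baseline limb never acts alone. If no fall is required and N is the lowest *post-baseline* value, a man who never falls has N ≥ B, and the baseline limb does separate work when N > B. The separate limb therefore suggests that no fall was intended. This is a pointer only: if N includes baseline, N ≤ B always and the limb is redundant under either reading.

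**The case against.** The best defence is that there is no real conflict. No section says a fall is required; *secondary* may be a label carried over from the endpoint name; the separate baseline limb fits a rule without a fall; and 6.4 presents itself as the place for definitions, so a programmer would go there first. The protocol, not seen here, may also settle the term. Much of this stands. It is why the point is an undefined and inconsistently used term, not a proven contradiction over steadily rising men. It does not clear the text, because intent has to be inferred, and following 6.4 to the letter brings in its own wording of 25% of baseline.

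That wording has a milder reading in 6.1.2, where the 25% can be taken as the size of the rise. In 6.4 the threshold is applied to PSA itself, so the mild reading is harder to sustain. Few programmers would implement it literally, but a definition should not rely on that.

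The size is also open to challenge. It rests on assumed growth and CV, and it nearly vanishes with no growth and little noise. Reading noise alone produces many events: with no growth and CV 10%, 65% have a rise by 2 years and 53% have one after a fall.

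A reader might infer that the choice of section could reverse the treatment comparison, or that it biases the comparison against enzalutamide. The documents do not support either. They give no PSA course for either arm, and only the surveillance arm was simulated. Treatment lasts one year, followed by a year off drug. If PSA recovers then (an assumption), the nadir limb could bring the 2-year enzalutamide incidence close to 100%, no lower than surveillance under either reading.

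**Conclusion.** The inconsistency is in the text and should be corrected. The event has two names, the baseline limb has two meanings, the absolute limb has two inequalities, and neither *secondary* nor the nadir is defined. The evidence leans towards a rule with no prior fall but does not settle it.

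If one analyst requires an earlier fall and another does not, the 2-year surveillance-arm incidence could differ by under 1 to about 77 percentage points over the assumed range of PSA growth and reading error. That enzalutamide subjects would be less affected rests on the expectation that their PSA falls first. The primary endpoint is untouched, and no change in the direction of any treatment comparison has been demonstrated.

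**What to change.** Before database lock, put one definition in Section 6.4 and use it in 3.1, 6.1.2 and 7.4.2.1:

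- PSA at least 25% *above* baseline, or at least 25% above nadir, or an absolute increase of at least 2 ng/mL from a stated reference value (baseline or nadir; name one).
- Nadir is the lowest value to date, including baseline. The baseline limb is then implied by the nadir limb; keeping it does no harm.
- No earlier fall is required. Delete *secondary*, or state that it adds no condition.

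Check this against the protocol first. If the protocol does require a prior fall, say so in 6.4, state what counts as a fall, and add the definition without a fall as a sensitivity analysis, because the requirement would be expected to remove events mainly from the surveillance arm.

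The cost is SAP wording and matching derivation code, plus one repeat analysis if the sensitivity analysis is needed. No new data are required.
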